5.5 Pharmacokinetic, Pharmacodynamic, Pharmacogenomic, and Other Biomarker Analyses

5.5.1 Pharmacokinetic Analyses

The Safety Analysis Set will be used for individual lenvatinib plasma concentrations and nivolumab serum concentrations listings. The PK Analysis Set will be used for the summaries of lenvatinib plasma concentrations and nivolumab serum concentrations, for summaries and listings of PK parameters of lenvatinib.

5.5.1.1 Plasma or serum Concentration and its PK Parameter Analysis

<Concentration>

Plasma concentration values for lenvatinib and serum concentration values for nivolumab will be summarized by dose level using summary statistics (n, mean, standard deviation [SD], median, minimum [min] and maximum [max]) by nominal time point.

Plasma concentrations of lenvatinib, serum concentrations of nivolumab will be listed for each subject by actual sampling time.

<PK Parameter>

PK parameters will be derived by non-compartmental analysis using WinNonlin software (version 6.2.1 or later) according to 302-104.00-MNL.

The following pharmacokinetic parameters for lenvatinib will be calculated: C_{max} , t_{max} , $AUC_{(0-t)}$, $AUC_{(0-t)}$, $AUC_{(0-inf)}$, $t_{1/2}$, CL/F , V_z/F , $C_{ss,max}$, $C_{ss,min}$, $t_{ss,max}$, $AUC_{(0-t)}$, CL_{ss}/F , $C_{ss,av}$, $R_{ac}(C_{max})$, $R_{ac}(AUC)$, PTF ratio and λ_z .

Other PK parameters may be calculated as appropriate.

Summary statistics will be tabulated for the PK parameters of lenvatinib by dose level. Summary statistics (n, mean, SD, median, min, and max) will be presented for all parameters (apart from t_{max} and $t_{ss,max}$ where mean and SD are not required). In addition, geometric mean and %CV will also be presented for all parameters apart from t_{max} and $t_{ss,max}$.

PK parameters of lenvatinib for each subject will be listed.

5.5.1.2 Pharmacokinetic Data Figures

The linear and semi-log plots of plasma concentration for lenvatinib and serum concentration for nivolumab versus actual time will be displayed by individual subjects. The actual time will be plotted on the X axis and the concentrations of lenvatinib and nivolumab will be plotted by dose level on the Y axis.

The linear and semi-log mean (+SD) plots of lenvatinib plasma concentration versus nominal time will be displayed. The nominal time will be plotted on the X axis and the mean (+SD)

will be plotted by dose level on the Y axis on the same graph by visit (Cycle 1 Day 1 and Cycle1 Day 15).

The linear and semi-log mean (+SD) plots of nivolumab serum concentration versus nominal time will be displayed. The nominal time will be plotted on the X axis and the mean (+SD) will be plotted on the Y axis on the same graph.

5.5.2 Pharmacodynamic, Pharmacogenomic, and Other Biomarker Analyses

The effect of lenvatinib-nivolumab combination therapy on soluble and/or tissue biomarkers will be summarized using descriptive statistics. This analysis will be performed only when relevant biomarkers are evaluated and the analysis is deemed necessary.

5.6 Safety Analyses

All DLT analyses will be performed on the DLT Analysis Set. All other safety analyses will be performed on the Safety Analysis Set by part. Safety data will be summarized using descriptive statistics (eg, n, mean, standard deviation, median, minimum, maximum for continuous variables; n [%] for categorical variables).

5.6.1 Extent of Exposure

The parameters to be summarized are defined as follows.

These parameters for extent of exposure will be computed and presented for lenvatinib alone and nivolumab alone, separately.

For lenvatinib:

- Number of cycles = The last cycle with at least one lenvatinib dosing
- Duration of treatment (days) = Last dosing date – first dosing date + 1
- Duration of treatment (months) = (Last dosing date – first dosing date + 1) / (365.25/12)
- Number of subject-month with study drug dosing = Sum of duration of treatment (months) per subjects
- Total number of doses = Sum of days with lenvatinib dosing
- Total doses (mg) = Sum of all the actual dose
- Dose intensity (mg / days) = Total doses / Duration of treatment (days)
- Relative dose intensity (%) = $100 \times \text{Dose intensity} / \text{starting planned dose (8 or 12 mg)}$

For nivolumab:

- Number of cycles = The last cycle with at least one nivolumab dosing
- Duration of treatment (days) = Last dosing date with nivolumab – first dosing date + 1
- Duration of treatment (months) = (Last dosing date with nivolumab – first dosing date + 1) / (365.25/12)
- Number of subject-month with study drug dosing = Sum of duration of treatment (months) per subjects
- Total number of doses = Sum of days with nivolumab dosing
- Total doses (mg) = Sum of all the actual dose derived by [240 (mg) x (Actual volume infused (ml) / volume to be infused (ml))]
- Dose intensity (mg / 2weeks) = Total doses / ((Last dosing date with nivolumab – first dosing date + 14) / 14)
- Relative dose intensity (%) = $100 \times \text{Dose intensity} / 240 \text{ (mg)}$

Number of cycles as combination therapy of lenvatinib and nivolumab will also be calculated and presented. The smaller number of cycles within a subject is defined as the number of cycle as combination therapy.

Furthermore, the following information of administration will also be summarized for both lenvatinib and nivolumab based on study medication data.

For lenvatinib, the number (percentage) of subjects who experienced a dose reduction and interruption will be summarized. For subjects who experienced a dose reduction, cycle of the first dose reduction will be summarized by descriptive statistics. Cycle of the first dose interruption will also be summarized in subjects who experienced a dose interruption. Frequency of dose reductions will be summarized by categories (1, 2, 3, ≥ 4). Frequency of dose interruptions will also be summarized by appropriate categories (e.g., 1, 2, 3, ≥ 4).

The date of dose reduction (from XX mg to YY mg, $XX > YY > 0$) is defined as the first date of planned dose of 0 mg followed by YY mg. The first date of 0 mg has to follow planned dose of XX mg. If the starting dose of YY mg does not follow 0 mg but XX mg, the first date of planned dose of YY mg is regarded as the date of dose reduction. Note that from 4 mg QD to 4mg QOD is also dose reduction.

The dose interruption is defined as the case where planned dose is 0 mg. The starting date of dose interruption is defined as the first date of planned dose of 0 mg following and followed by same dose level (> 0 mg). For example: 12 mg followed by 0 mg and followed by 12 mg; 8 mg followed by 0 mg followed by 8 mg. Successive days with planned dose of 0 mg is counted as one dose interruption event. If after dose 0 mg, the subject discontinued from lenvatinib permanently, it is not regarded as a drug interruption (but as a drug discontinuation).

An illustration for dose reduction and interruption in a subject is shown in Figure 2.

[figure not shown]

Figure 2 Dose reduction and interruption for lenvatinib

For nivolumab, the number (percentage) of subjects who experienced a dose interruption will be summarized. Cycle of first dose interruption will be summarized by descriptive statistics in subjects who experienced a dose interruption. Frequency of dose interruptions will be summarized by appropriate categories (e.g., 1, 2, 3, ≥ 4).

The dose interruption is defined as the case where planned dose of 0 mg. Successive dates with planned dose of 0 mg is counted as one dose interruption event, and the first date with

planned dose of 0 mg is defined as the starting date of dose interruption. If after dose 0 mg, the subject discontinued from nivolumab permanently, it is not regarded as a drug interruption (but as a drug discontinuation).

Subject data listings will be provided.

5.6.2 Dose Limiting Toxicity

The number and percentage of subjects with DLT will be calculated. DLT will also be summarized per type of toxicity.

Subject data listings will be provided.

5.6.3 Adverse Events

The AE verbatim descriptions (investigator terms from the CRF) will be classified into standardized medical terminology using the Medical Dictionary for Regulatory Activities (MedDRA version 20.1 or later). Adverse events will be coded to the MedDRA lower level term (LLT) closest to the verbatim term. The linked MedDRA preferred term (PT) and primary system organ class (SOC) will also be captured in the database.

A treatment-emergent adverse event (TEAE), defined in the [section 8.3](#), will be included in summary tables. All AEs, treatment emergent or otherwise, will be presented in subject data listings.

Treatment-related TEAEs include those events considered by the investigator to be related to study treatment.

A subject will be counted only once within a SOC and PT, even if the subject experienced more than 1 TEAE within a specific SOC and PT.

An overview table, including the incidence of and the number of subjects with TEAEs, Treatment-related TEAEs, TEAEs with grade 3 or above, serious adverse events (SAEs), deaths, and TEAEs that led to discontinuation of lenvatinib, discontinuation of nivolumab, dose reduction of lenvatinib, dose interruption of lenvatinib and dose interruption of nivolumab will be provided.

The incidence of below events will be reported as the number (percentage) of subjects with TEAEs by MedDRA SOC and PT.

- TEAEs
- TEAEs by the highest CTCAE grade
- TEAEs grade 3 or above
- Serious TEAEs
- Treatment-related TEAEs
- Treatment-related TEAEs by the highest CTCAE grade
- Treatment-related TEAEs grade 3 or above
- Treatment-related serious TEAEs
- TEAEs leading to discontinuation of lenvatinib

- TEAEs leading to dose reduction of lenvatinib
- TEAEs leading to dose interruption of lenvatinib
- TEAEs leading to discontinuation of nivolumab
- TEAEs leading to dose interruption of nivolumab

All deaths will also be summarized by primary reasons of deaths (progressive disease, AEs, others), deaths within 30 days of last dose of study drug, deaths >30 days of last dose of study drug, and treatment-related deaths.

Subject data listings of all deaths, SAEs, AEs leading to death, discontinuation of lenvatinib, discontinuation of nivolumab, dose reduction of lenvatinib, dose interruption of lenbatinib and dose interruption of nivolumab will be provided.

5.6.4 Laboratory Values

Laboratory results will be summarized using Système International (SI) units. For all quantitative parameters, the actual value and the change from baseline to each postbaseline visit will be summarized by visit using summary statistics. Qualitative parameters will be summarized by number and percentage of subjects, and changes from baseline to each postbaseline visit will be reported using shift tables. Percentages will be based on the number of subjects with both nonmissing baseline and relevant postbaseline results.

Box plot display will be used to show the longitudinal change of the parameters by visit.

Laboratory test results will be assigned a low/normal/high (LNH) classification according to whether the value is below (L), within (N), or above (H) the laboratory parameter's reference range. The result of LNH classification will be provided in a subject data listing.

Laboratory parameters will be graded by CTCAE ver. 4.03 in the [section 13](#). Changes from CTCAE grade at baseline to each postbaseline visit and worst postbaseline will be reported using shift tables. CTCAE will also be used to identify subjects with Treatment-emergent markedly abnormal laboratory value (TEMAV). The number (percentage) of subjects with TEMA (markedly abnormal high/low) will be summarized for each visit and overall study period. The changes from baseline to each postbaseline visit and overall study period will also be reported using shift tables. The TEMA will be defined in the [section 8.3](#).

Subject data listings will be provided.

5.6.5 Vital Signs

Summary statistics for vital signs parameters (diastolic and systolic blood pressure, pulse, and temperature), weight, and SPO₂ and changes from baseline will be presented by visit.

Box plot display will be used to show the longitudinal change of the parameters by visit.

Subject data listings will be provided.

5.6.6 Electrocardiograms

The results of ECG assessments performed at each visit will be evaluated. Summary statistics for ECG parameters (Heart Rate, RR, PR, QRS, QT, and QTcF) and changes from baseline will be presented by visit.

Shift tables will present changes from baseline in ECG interpretation (categorized as normal; abnormal, not clinically significant; and abnormal, clinically significant) to each visit.

In addition, the number (percentage) of subjects who met below criteria at least once in QTcF will be presented:

Absolute QTcF interval prolongation:

- QTcF interval >450 ms
- QTcF interval >480 ms
- QTcF interval >500 ms

Change from baseline in QTcF interval:

- QTcF interval increases from baseline >30 ms
- QTcF interval increases from baseline >60 ms

Subject data listings will be provided.

5.6.7 Other Safety Analyses

LVEF

Descriptive statistics for LVEF and LVEF changes from baseline assessed by MUGA scans or echocardiograms will be summarized by visit.

Subject data listings will be provided.

ECOG PS

The number (percentage) of subjects for each category of ECOG PS will be summarized by visit. The highest postbaseline scale of ECOG PS for each subject will also be summarized.

Subject data listings will be provided.

5.7 Other Analyses

Immunogenicity

All immunogenicity analyses will be performed using the Safety Analysis Set. The percentage and frequency of expression will be calculated for serum anti-nivolumab

antibodies (ADA). If anti-nivolumab antibody develops, presence of neutralizing antibody will be summarized.

Subject data listings will be provided.

5.8 Exploratory Analyses

No exploratory analyses are planned for this study.

6 INTERIM ANALYSES

No interim analysis will be conducted.

7 CHANGES IN THE PLANNED ANALYSES

A summary of all major additions, changes and deletions in the planned analyses described in the protocol will be provided in this section.

CCI

8 DEFINITIONS AND CONVENTIONS FOR DATA HANDLING

The data will be handled as follows. The sponsor will determine how to handle all data prior to data base lock.

8.1 General Data Handling

Definition of Baseline data

Baseline is defined as the last non-missing value observed prior to the first dose of study treatment for a given parameter.

Definition of Change from Baseline, Percent Change from Baseline

Change from baseline is defined as post-baseline value minus baseline value.

Percent change from baseline is defined as follows:

$$\% \text{ Change from baseline} = (\text{Change from baseline} / \text{Baseline}) * 100\%$$

For any Baseline value of 0, the subject's corresponding percent change from baseline will not be included in the summary statistics table.

8.2 Efficacy Data Handling

Handling of missing data for tumor assessment result

For the analysis of ORR, DCR and CBR, subjects with missing response status (subjects whose baseline is missing and/or no adequate post-baseline tumor assessments result) will be coded as non-responders on Efficacy Analysis Set.

Rules for missing dates of tumor assessment or death

In case of dates missing in adverse event and concomitant medication collection following rules will be followed.

Data of tumor assessment result after documented PD or discontinuation from treatment

For the analysis of tumor assessment relevant efficacy endpoints, tumor assessment result after PD or final observation visit (for non-PD patients) are excluded from the analyses, but included in subject data listing.

8.3 Safety Data Handling

Treatment-emergent adverse event

A treatment-emergent adverse event (TEAE) is defined as an AE that emerges during the time from the first dose of study drug to 30 days following the last dose of study drug, having been absent at pretreatment (Baseline) or

- Reemerged during treatment, having been present at pretreatment but stopped before treatment, or
- Worsened in severity during treatment relative to the pretreatment state, when the AE was continuous.

Adverse Events

Adverse Events with incomplete start dates will be considered treatment emergent if:

- a. Day and month are missing and the year is equal to or after the year of the first dose date;
- b. Day is missing, and the year is after the year of the first dose;
- c. Day is missing and the year is equal to the year of the first dose date and the month is equal to or after the month of the first dose date;
- d. Year is missing;
- e. Complete date is missing.

Concomitant Medications

Medications will be considered concomitant if:

- a. Day and month are missing and the year is equal to or after the year of the first dose date;
- b. Day is missing, and the year is after the year of the first dose;
- c. Day is missing and the year is equal to the year of the first dose date and the month is equal to or after the month of the first dose date; or
- d. Year is missing;
- e. Complete date is missing.

TEMAV (Treatment-Emergent Markedly Abnormal Value)

Treatment-emergent markedly abnormal laboratory value (TEMAV) is defined as a postbaseline laboratory value with grade 3 or higher, and with a grade increase from baseline. (ie., Increasing grade 0 to 3 or higher, grade 1 to 3 or higher, grade 2 to 3 or higher, grade 3 to 4 or 5, grade 4 to 5.)

Handling of below lower quantification values in laboratory results

In the cases where laboratory result contains below lower quantification (BLQ) value, it will be replaced to the lower limit value of quantification (LLOQ) for summary tables.

The priority of use for blood pressure

For systolic and diastolic blood pressures, additional confirmatory assessment will be done more than 60 minutes after initial assessment, if necessary. In the case where there are both the initial and confirmatory assessment results in a day, confirmatory one will be used.

Calculation of creatinine clearance

To calculate a creatinine clearance (mL/min), the Cockcroft & Cault formula will be used.

Males: $((140 - \text{age (years)}) \times \text{weight (kg)}) / (\text{Creatinine (serum:mg/dL}) \times 72)$

Females: $((140 - \text{age (years)}) \times \text{weight (kg)} \times 0.85) / (\text{Creatinine (serum:mg/dL}) \times 72)$

Visit Windows

The purpose of visit windows is to provide a single record per subject per visit for the calculation of descriptive statistics for safety parameters (e.g., laboratory values and vital signs, etc.) per scheduled visit, and change from baseline per visit. Other safety analyses (e.g., worst grade laboratory results) will include all observations.

The observation closest to the target date will be used in by visit summaries. If two or more observations have the same distance to the target visit day, the one that has the highest CTCAE grade or is furthest away from the normal range will be used for summary tables. If the multiple data in the same distance to the target date are in the same range from normal value, the data measured at an earlier date will be used for summary tables.

The visit window is applied for safety assessment item which is scheduled at each visit.

Analysis visit	Target Day	Visit Window	
		Start Day of Visit Window	End Day of Visit Window
Cycle 1 Day 8	Cycle 1 Day 1 + 7	Cycle 1 Day 1 + 5	Cycle 1 Day 1 + 9
Cycle 1 Day 15	Cycle 1 Day 1 + 14	Cycle 1 Day 1 + 12	Cycle 1 Day 1 + 16
Cycle 1 Day 22	Cycle 1 Day 1 + 21	Cycle 1 Day 1 + 19	Cycle 1 Day 1 + 23
Cycle 2 Day 1	Cycle 1 Day 1 + 28	Cycle 1 Day 1 + 28	Cycle 1 Day 1 + 31
Cycle 2 Day 8	Cycle 1 Day 1 + 35	Cycle 1 Day 1 + 32	Cycle 1 Day 1 + 38
Cycle 2 Day 15	Cycle 1 Day 1 + 42	Cycle 1 Day 1 + 39	Cycle 1 Day 1 + 45
Cycle 2 Day 22	Cycle 1 Day 1 + 49	Cycle 1 Day 1 + 46	Cycle 1 Day 1 + 52
Cycle n Day 1 ($n \geq 3$)	Cycle n Day 1 + 28 x (n-1)	Cycle n Day 1 + 28 x (n-1) - 3	Cycle n Day 1 + 28 x (n-1) + 3

Cycle n Day 8 (n ≥ 3)	Cycle n Day 1 + 28 x (n-1) + 7	Cycle n Day 1 + 28 x (n-1) + 4	Cycle n Day 1 + 28 x (n-1) + 10
Cycle n Day 15 (n ≥ 3)	Cycle n Day 1 + 28 x (n-1) + 14	Cycle n Day 1 + 28 x (n-1) + 11	Cycle n Day 1 + 28 x (n-1) + 17
Cycle n Day 22 (n ≥ 3)	Cycle n Day 1 + 28 x (n-1) + 21	Cycle n Day 1 + 28 x (n-1) + 18	Cycle n Day 1 + 28 x (n-1) + 24
End of Treatment	30 days after last dose	Date of last dose	Date of last dose + 37

C1D1 is the day of first dosing.

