9.5.1.5.1 ADVERSE EVENTS

An AE is any untoward medical occurrence in a subject. An AE does not necessarily have a causal relationship with the medicinal product. For this study, the study drugs are lenvatinib and nivolumab.

The criteria for identifying AEs in this study are:

- Any unfavorable and unintended sign (including an abnormal laboratory finding), symptom, or disease found after the time of informed consent, whether or not considered related to the investigational product (Note: Every sign or symptom should not be listed as a separate AE if the applicable disease [diagnosis] is being reported as an AE)
- Any new disease or exacerbation of an existing disease. However, worsening of the primary disease should be captured under efficacy assessments as disease progression rather than as an AE.
- Any deterioration in nonprotocol-required measurements of a laboratory value or other clinical test (eg, ECG or x-ray) that results in symptoms, a change in treatment, or discontinuation of study drug
- Recurrence of an intermittent medical condition (eg, headache) not present pretreatment (Baseline)
- An abnormal laboratory test result should be considered an AE if the identified laboratory abnormality leads to any type of intervention, withdrawal of study drug, or withholding of study drug, whether prescribed in the protocol or not

All AEs, regardless of relationship to study drug or procedure, should be collected beginning from the time the subject signs the study ICF through the 30 days after the last dose or until the subject initiates new anticancer therapy, whichever is earlier. SAEs will also be collected for 30 days after the last dose or until the subject initiates new anticancer therapy, whichever is earlier.

Any laboratory abnormality considered to constitute an AE should be reported on the CRF. Abnormal laboratory values should not be listed as separate AEs if they are considered to be part of the clinical syndrome that is being reported as an AE. It is the responsibility of the investigator to review all laboratory findings in all subjects and determine if they constitute an AE. Medical and scientific judgment should be exercised in deciding whether an isolated laboratory abnormality should be classified as an AE.

Abnormal ECG (QTcF) results, if not otherwise considered part of a clinical symptom that is being reported as an AE, should be considered an AE if the QTcF interval is more than

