9.5.4.1 Reporting of Serious Adverse Events

All SAEs, regardless of their relationship to study treatment, must be reported on a completed SAE form as soon as possible but no later than 1 business day from the date the investigator becomes aware of the event.

SAEs, regardless of causality assessment, must be collected through 30 days after last dose or until the subject initiates new anticancer therapy, whichever is earlier. All SAEs must be followed to resolution or, if resolution is unlikely, to stabilization. Any SAE judged by the investigator to be related to the study drug or any protocol-required procedure should be reported to the sponsor regardless of the length of time that has passed since study completion.

The detailed contact information for reporting of SAEs is provided in the Attachment.

It is very important that the SAE report form be filled out as completely as possible at the time of the initial report. This includes the investigator or subinvestigator's assessment of causality.

Any follow-up information received on SAEs should be forwarded from the investigator to the sponsor within 1 business day of its receipt. If the follow-up information changes the investigator's assessment of causality, this should also be noted on the follow-up SAE form.

Preliminary SAE reports should be followed as soon as possible by detailed descriptions including copies of hospital case reports, autopsy reports, and other documents if requested by the sponsor.

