8.3 Safety Data Handling

Treatment-emergent adverse event

A treatment-emergent adverse event (TEAE) is defined as an AE that emerges during the time from the first dose of study drug to 30 days following the last dose of study drug, having been absent at pretreatment (Baseline) or

- Reemerged during treatment, having been present at pretreatment but stopped before treatment, or
- Worsened in severity during treatment relative to the pretreatment state, when the AE was continuous.

Adverse Events

Adverse Events with incomplete start dates will be considered treatment emergent if:

- a. Day and month are missing and the year is equal to or after the year of the first dose date;
- b. Day is missing, and the year is after the year of the first dose;
- c. Day is missing and the year is equal to the year of the first dose date and the month is equal to or after the month of the first dose date;
- d. Year is missing;
- e. Complete date is missing.

Concomitant Medications

Medications with incomplete end dates will be considered concomitant if:

- a. Day and month are missing and the year is equal to or after the year of the first dose date;

- b. Day is missing, and the year is after the year of the first dose;
- c. Day is missing and the year is equal to the year of the first dose date and the month is equal to or after the month of the first dose date; or
- d. Year is missing;
- e. Complete date is missing.

OR; complete end dates is between the date of first study dose and date of last study dose even if the start date of medications is incomplete.

TEMAV (Treatment-Emergent Markedly Abnormal Value)

Treatment-emergent markedly abnormal laboratory value (TEMAV) is defined as a postbaseline laboratory value with grade 3 or higher, and with a grade increase from baseline. (ie., Increasing grade 0 to 3 or higher, grade 1 to 3 or higher, grade 2 to 3 or higher, grade 3 to 4 or 5, grade 4 to 5.)

Handling of below lower quantification values in laboratory results

In the cases where laboratory result contains below lower quantification (BLQ) value, it will be replaced to the lower limit value of quantification (LLOQ) for summary tables.

The priority of use for blood pressure

For systolic and diastolic blood pressures, additional confirmatory assessment will be done more than 60 minutes after initial assessment, if necessary. In the case where there are both the initial and confirmatory assessment results in a day, confirmatory one will be used.

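### SAP 8.3 flags adverse events with incomplete start dates as treatment-emergent without looking at a known stop date, so an event that ended before the first dose can enter the TEAE tables

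*SAP*

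**What the plan says.** The SAP file holds two versions. This point concerns the current one, whose reference list cites the December 2018 FDA guidance. The adverse event wording discussed here is the same in the other version.

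- **Definition (SAP 8.3).** A TEAE is "an AE that emerges during the time from the first dose of study drug to 30 days following the last dose of study drug". The event must also not have been present at baseline. Two bullets add re-emergence and worsening; the second reads "Worsened in severity during treatment relative to the pretreatment state, when the AE was continuous".
- **Partial dates (SAP 8.3).** "Adverse Events with incomplete start dates will be considered treatment emergent if" any of items a to e is met. Item b reads "Day is missing, and the year is after the year of the first dose". Item c begins "Day is missing and the year is equal to the year of the first dose date and the month is equal to or after"; it compares against the first-dose month. Item a does the same by year when day and month are both missing. Items d and e apply whenever the year, or the whole date, is missing.
- **Medications (SAP 8.3, same section).** A medication whose start date is incomplete counts as concomitant when its "complete end dates is between the date of first study dose and date of last study dose". The adverse event rule has no matching line.
- **Collection (Protocol 9.5.1.5.1).** Adverse events "should be collected beginning from the time the subject signs the study ICF through the 30 days after the last dose", or until new anticancer therapy if that comes first. Protocol 9.1.3.1 allows consent up to 28 days before the first dose.
- **Late SAEs (Protocol 9.5.4.1).** An SAE judged related to study drug or to a protocol-required procedure "should be reported to the sponsor regardless of the length of time that has passed since study completion".
- **Use (SAP 5.1.1 and 5.6.3).** Adverse events are among the primary endpoints, and the summary tables are built from TEAEs.

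**The concern.** A partial-date rule should settle cases in which the timing is unknown. Here, meeting one item is enough for the flag, so the rule also decides cases in which the database already holds the answer. If the stop date is complete and precedes the first dose, the event was over before any study drug was given. It cannot meet the definition a few lines above, yet the rule counts it.

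The stretch between consent and first dose is when such events are recorded. It covers screening procedures and, for some Part 2 subjects, a fresh tumor biopsy. Whether an event from that stretch appears in a TEAE table should depend on when it happened, not on whether the day of onset was written down.

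The rule also has no limit at the far end: the last dose date does not appear in items a to e.

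**Working it through.** The plan gives no figure for this point. Its only computed figures, the detection probabilities in SAP section 4, reproduce (1 − 0.90^20 = 87.8%, 1 − 0.85^20 = 96.1%, 1 − 0.80^20 = 98.8%) but play no part here.

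**1. The rule applied to constructed cases.** The dates are assumed: first dose 20 March 2019, last dose 10 September 2019. The definition's window then runs from 20 March to 10 October 2019.

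| Start date recorded | Other information | By the definition | By items a to e |
|---|---|---|---|
| March 2019, day missing | Stopped 12 March 2019 | Not a TEAE: ended before first dose | TEAE (item c) |
| February 2019, day missing | Stopped 27 February 2019 | Not a TEAE | Not a TEAE |
| January 2020, day missing | None needed: the whole month is after 10 October 2019 | Not a TEAE | TEAE (item b) |

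In the first row the rule and the definition disagree although the stop date settles the matter. Under items d and e the same result follows without even a start month. The second row shows that the rule does screen out partial dates before the first-dose month.

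**2. How far the late end reaches.** Routine collection and the SAP window both stop at 30 days after last dose. An event that began on or before last dose + 30 has a start month whose first day is no later than that date. Its month therefore cannot lie wholly outside the window. Enumerating every last-dose date in 2018–2020 with onsets 0 to 30 days later found 0 such cases. For onsets 31 to 37 days after last dose (the SAP's End of Treatment visit window runs to day 37), 13% had a start month wholly outside. The third row therefore needs a late related SAE, or an event recorded past the collection period, that is entered in the AE data with its day missing.

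**3. Effect of one misclassified subject.** SAP 5.6.3 counts a subject once per preferred term, so a row moves only if that subject has no other TEAE in the term.

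- Part 2, all subjects: 1/20 = 5.0 points.
- Part 1, all subjects: 1/6 = 16.7 points.
- SAP section 5 also reports the 8 mg and 12 mg groups separately. At the Part 2 floor of 5 subjects per group, 1/5 = 20 points.

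These are the sizes of any single-subject change. They are not estimates of how often the error occurs.

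**4. Where the window ends.** SAP 8.3 ends it at 30 days after last dose. Protocol 9.7.1.8.2 ends it at 30 days or at new anticancer therapy, whichever comes first. A check against the end of the window cannot be programmed until one of these is chosen.

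**The case against.** The case for leaving the rule alone is reasonable in several respects.

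- **Over-counting is the cautious default in a safety table.** This stands where the stop date is unknown or falls on or after the first dose, because the timing is then uncertain. It does not stand where the recorded stop date precedes the first dose.
- **Nothing is decided on it.** SAP 5.3.3 plans no statistical comparison. Part 1 tolerability rests on DLTs in the DLT Analysis Set. All adverse events are listed whether or not they are treatment-emergent, so with about 26 subjects a wrong flag can be found. All of this stands and limits the size of the point.
- **Programming rules are in separate documents (SAP section 9), and the sponsor settles data handling before lock (SAP section 8).** A stop-date check may exist there. That does not correct a rule in the SAP that says otherwise.

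A reader might also infer more than the documents support.

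- **That late events enter freely, however long after last dose.** The wording sets no limit, but Protocol 9.5.1.5.1 and 9.5.4.1 stop routine collection at 30 days. The exception for related SAEs concerns reporting to the sponsor. The documents do not say that such reports enter the CRF data behind the tables.
- **That half or more of pre-dose events are misflagged.** With first-dose day d uniform over a 30-day month, the mean of min(d−1, 28)/28 is 0.52 and of min(d−1, 14)/14 is 0.75. These are the shares of the 28-day consent and 14-day screening periods that fall in the first-dose month. They take the day as already missing and do not require a known pre-dose stop date, so they do not measure this error.
- **That worsening soon after last dose is lost.** The two bullets speak only of the treatment period, while new events count for 30 more days. The lead clause may be meant to govern both. For laboratory values, the TEMAV definition and the worst-postbaseline shift tables are not limited to the treatment period. This is an ambiguity separate from the partial-date rule.

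**Conclusion.** The point holds for the stop date. As written, SAP 8.3 classifies as treatment-emergent an event that the data show was over before the first dose, and this contradicts the definition in the same section. The late-end gap is real in the wording but should matter rarely. It depends on a related SAE, or an event recorded past the collection period, reaching the AE data without a day of onset.

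The documents do not say how many start dates are incomplete. I assume few, so the likely effect is a handful of table entries at most, each worth 5 points in a Part 2 row under the condition stated above. The direction is over-counting. The tolerability decision and the study's conclusions are not at risk. It is still worth correcting before database lock, because the tables concerned report a primary endpoint and the medication rule beside it already uses a complete end date when the start date is incomplete.

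**What to change.** In the current SAP 8.3, add to items a to e: *unless the stop date, or its known part, shows that the event ended before the first dose, or the known part of the start date shows that it began after the end of the TEAE window.* Where neither date settles the matter, the present default of counting the event stays.

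State one end for the window, reconciling SAP 8.3 (30 days after last dose) with Protocol 9.7.1.8.2 (30 days or new anticancer therapy, whichever comes first), and use it throughout.

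Optionally, use that same window in the two bullets on re-emergence and worsening, so that two programmers would code them alike.

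The cost is a few lines of SAP text and a small change to the TEAE flag, with no new data. By the argument in step 2 of the working, the late-end check with the 30-day end removes no event that truly began within 30 days of last dose.
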